1.1 Background

Hepatitis C virus (HCV) infection is a chronic, debilitating disease that affects 170 million people globally and about 3.9 million people in the U.S. [1]. HCV infection is the most common blood-borne illness in the U.S [2], and is especially prevalent among those with chronic kidney disease (CKD). The estimated prevalence of HCV in hemodialysis patients in the U.S. is 8% [3], almost five times greater than the prevalence in the general US population [4]. Some individuals with untreated HCV can develop serious complications including cirrhosis, liver failure, and/or hepatocellular carcinoma [5].

Among patients with CKD, the presence of HCV can significantly impact both quality of life and health outcomes. Patients with CKD who are HCV+ may have an increased risk of death, loss of kidney function, and kidney transplant failure [5-11]. HCV infection has been linked with lower quality of life in patients on dialysis, and may be particularly detrimental to patients' mental health [12].

The goal of therapy for chronic HCV infection is a sustained virologic response (SVR) where the disease is no longer detected for six months (24 weeks) following discontinuation of therapy [13]. SVR reduces the likelihood of cirrhosis of the liver, liver cancer, the need for liver transplantation and overall death rates among patients with CKD [14-17]. As a result, national and international guidelines suggest that HCV+ patients with CKD should consider anti-viral treatment for their HCV [18].

Despite these potential benefits, few patients with CKD receive treatment for their HCV infection [19]. Early medications for HCV infection included interferon, Pegylated interferon and/or ribavirin as treatment options available for HCV infected patients. These drugs were not always effective, eliminating HCV from only 14%-63% of patients [20]. Furthermore, many patients experienced serious side effects from treatment and reduced their doses or discontinued treatment on these medications [21, 22]. Because these drugs are renally eliminated, treating HCV in CKD patients was especially challenging, and many patients with CKD and their clinicians felt that the potential benefits of treatment did not outweigh the potential risks. As a result, as few as 1% of HCV+ CKD patients were prescribed antiviral medications [2].

In recent years, direct-acting antivirals (DAAs) specifically designed to attack HCV proteins were developed and became available as treatment options for patients with HCV infection. DAAs have a much higher SVR (>95%) and relatively few toxicities compared to earlier treatments [23, 24]. They also have easier dosing regimens and fewer interactions with other medications used to treat patients with comorbidities [24]. Studies suggest that patients with mild to moderate renal impairment tolerate treatment with DAAs well, and have many positive outcomes from these treatments. However, they may face complicated decisions about whether to consider pre-emptive kidney transplants or other treatments before or after treating their HCV.

In addition, some patients with significant renal impairment (eGFR <30) and comorbidities, decisions about whether and when to treat HCV are complex. Factors such as patients' CKD severity, genotype, transplant status (e.g., on-waiting list for kidney transplant, which can lead to

decisions about whether treatment will delay kidney transplant), and comorbidity status can influence treatment decisions and outcomes. Patients' subjective preferences for the tradeoffs between potential benefits and harms of treatment can significantly impact choices. Patients' insurance coverage and potential out-of-pocket costs can also impact their access and adherence to treatment [3] [4]. In order to make treatment decisions, patients must balance each of these factors, as well as advice from multiple clinicians, including nephrologists, hepatologists, and sometimes a primary care provider.

Given the variety and complexity of treatment options that depend on patients' clinical characteristics and personal preferences, interventions are needed to better prepare patients to discuss options with clinicians. Patient decision aids (DAs) are designed to help patients understand complex health options and take an active role in decision-making. DAs differ from education materials because of their detailed, specific, and personalized focus on options, outcomes, probabilities, and patients' values. DAs have been shown to reduce decisional conflict, increase patient's knowledge of treatment options, lower decision regret, increase patient involvement in decisions, reduce patient indecision concerning treatment, and increase the probability that treatment decisions will be consistent with patients' values [25].

1.2 Rationale

This project has the potential to improve clinical practice in several ways. We will be addressing a critical decision that patients and clinicians face about treatment options among patients with HCV and CKD. Current available evidence is inadequate to suggest one dominant treatment plan. Our project will help patients and clinicians weigh the evidence and consider patients' preferences to support patients through this complex decision. To our knowledge, there is limited literature on ways to support patients' decisions about this topic and no available decision tool to facilitate this process.

In addition, our project will incorporate physician and patient stakeholder input in the design of the DA such that the decision incorporates patients' preferences and clinical characteristics that impact outcomes. We will pilot test it to demonstrate its effect on decision quality. This process of gaining stakeholder input from individuals outside the development process and pilot testing it with patients is consistent with international guidelines for decision aid development [26], and ensures that our tool is relevant to end users.

Finally, there is variation in how clinicians approach this decision about whether and when to treat HCV among advanced CKD patients. A successful DA could be disseminated in a future study to help incorporate patient preferences into this decision across regions. Including stakeholders from different geographic regions makes our project more suitable for wider scale dissemination, and it will be adaptable for various clinics.

2 Objectives

Aim 1: To develop a decision aid (DA) for patients with Hepatitis C virus and chronic kidney disease to support their decisions about whether, when, and how to treat each illness.

Aim 2: To pilot test the DA to determine its efficacy, usability, and likelihood of using it in routine practice

3 Methodology

We will make the DA available to complete via tablet PCs at the clinic to reduce bias in recruiting patients who are familiar with computers and the Internet. However, patients who want to see the information on paper can opt to do so given the age of this population and variations in comfort using computers. Patients will be able to review the DA content at any point, and can take home a printed summary of the information so that they can review a summary with caregivers and/or their clinician. The summary will also be placed in their medical chart so that the clinicians can use it to personalize discussions. We will work with our patient and clinician stakeholders to identify when the optimal timing will be for patients to complete this tool without disrupting clinic flow. We will conduct informal usability testing with 10 additional patients to ensure that wording and formatting is clear to patients. These patients will not be included in Aim 2 so as not to bias Aim 2 participants.

Aim 2 Methods: The goal of Aim 2 is to pilot test the DA to determine its efficacy and the likelihood of using it in routine practice. We will pilot this with 70 patients using a within subjects design. Outcomes will include change in decisional conflict, change in decision self-efficacy, change in knowledge about HCV treatment risks and benefits among patient with CKD, and the match between patients' intended choice and their preferences.

A quasi-experimental design was chosen to examine within group (pre-post use of the DA) outcomes. We considered conducting a randomized trial. However, randomizing individual patients or clinicians might lead to an underestimation of the effect of the DA, as the DA would likely contaminate standard procedures. Moreover, given the size and scope of this pilot project, our goal is to demonstrate feasibility and preliminary efficacy which can be accomplished at our institution through a within subjects design.

3.2 Study Population

There will 100 participants recruited for the study in total. Of the total study population, 70 participants will be a part of aim 2 of our study and the remaining 30 participants will be participating in aim 3. For aim 2, patients will be recruited beginning November 2017 and lasting for 7 months. There are approximately 2600 patients in our CKD clinic (1552 with eGFR < 60, 560 with eGFR < 30) and over 500 dialysis patients. We also follow renal transplant patients in a transplant clinic. About 300 of these patients also have HCV. Based on these numbers, recruiting 70 patients in this time frame is feasible and can provide us with pilot data to evaluate our decision tool prior to a future randomized trial assessing effectiveness of the tool on clinical decision-making.

3.3 Inclusion Criteria

Aim 2 - Eligibility Criteria:

- Over the age of 18
- English-speaking
- Have HCV infection of any genotype
- And a diagnosis of CKD (we will stratify by GFR <30 and GFR >30).

3.4 Exclusion Criteria

Exclusion criteria include:

- Patients with self-reported or observed unstable medical or psychiatric condition, which would preclude providing consent or participating in the study
- Patients with any of the following:
 - Decompensated cirrhosis
 - Hepatocellular carcinoma
 - Post-liver transplantation

4 Variables and Measurement

4.1 Study Outcomes

- **Knowledge:** Similar to knowledge items used when designing DAs[37-39] and assessing decision quality[40], we will develop knowledge items based on information that is considered essential to making treatment decisions (e.g. understanding terms, understanding facts that differentiate options)[41]. Questions will be asked using true/ false/ unsure responses. Total number of correct responses to the items will be calculated. One point will be given for each correct response and zero for unsure or incorrect responses; answers will be expressed as percent correct. Similar scales have been used in other DA trials [38, 39] and have good internal consistency (Cronbach's alpha coefficients range from 0.82 – 0.83) [37].

Decisional Conflict: The Decisional Conflict Scale [42] (DCS) is a validated and widely-used measure of uncertainty about decisions. We will administer the 4-item SURE Test version of the DCS [42] to assess whether individuals feel they have enough information to make a choice, are clear about their values for risks and benefits of their choice, and feel they have enough support to make a choice. Items are scored as 1 (yes) or 0 (no). If the total score is less than 4, it indicates the probability that a patient experiences clinically significant decisional conflict.

- **Decision Self-Efficacy:** We will use the lower literacy version of the Decision Self-Efficacy Scale [43], a validated measure of an individual's self-confidence or belief in their ability to make a decision. Individuals are asked to rate on a three-item scale how confident they feel taking actions involved in making an informed choice (e.g., gathering information, asking questions, and expressing opinions). This scale has been validated and used to study health literacy and shared decision making among patients and lower SES populations among others [43-46]. It has high levels of internal consistency (mean Cronbach's alpha = 0.86) [43] and correlates with feeling informed, supported, and knowledgeable about decisions [43].

- **Usability:** After participants use the DA, they will complete the 10-item System Usability Scale (SUS [47]) to measure the DA's usability. We will also ask clinicians to fill out this measure after the end of the study.

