6.1.1 Administrative Procedures

6.1.1.1 Recruitment and Procedures

Aim 2- The goal of Aim 2 is to pilot test the DA to determine its efficacy and the likelihood of using it in routine practice. Eligible patients will be determined by the outpatient EMR (AllScripts). Once patients have been identified, their hepatologist or nephrologist will briefly describe the project and gauge patients' interest in participating. The project coordinator will then reach out to interested patients to describe the project in further detail and obtain informed consent. Patients will complete a brief pre-test questionnaire assessing socio-demographics, health literacy, knowledge, decisional conflict, and decision self-efficacy. All measures were chosen based on their short length so as not to burden participants. We have used a similar recruitment strategy and measures in past projects, and the procedures did not disrupt patient flow or introduce burden on patients [35, 36]. We will document CKD stage, dialysis status (yes/no), stage of fibrosis of the liver, whether or not the patient has tried using a DAA in the past to treat HCV, and presence of comorbidities (diabetes, heart disease, high blood pressure, HIV) to use for tailoring health information in the decision tool. This information will be collected from patients and clinicians and verified in the medical record with patients' consent.

Next, we will provide patients with the DA through tablet PCs on-site, brief training on how to use the tablets, and we will allow patients to view the DA. Patients can opt to view it on paper if they are uncomfortable with computers. They can take home a printed summary of the information to review at home before meeting with their clinician. The summary will also be placed in the patient's chart. After viewing the DA, patients will complete post-test measures of knowledge, decisional conflict, and decision self-efficacy. Recruitment will occur over 12 months. Patients will be provided with a \$20 gift card for participation and will have the added benefit of using the DA. We anticipate the pilot test to take about 30-45 minutes.

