8.1 Statistical Methods

Aim 2 Analytic Methods: For all analyses, descriptive statistics (e.g., frequencies, tendencies, variability) and diagnostic plots will be completed on all variables. Data will be examined for outliers and tested as appropriate for normality, linearity, and homoscedasticity. Appropriate corrective strategies, such as transformations, use of robust methods, or data reduction, will be used if problems are identified. These preliminary analyses are necessary to ensure high quality data and to test assumptions of the proposed models. We will also compare basic demographic and clinical characteristics between study enrollees and eligible refusers to characterize the representativeness of the included patients. We will also examine within group differences in our outcomes (knowledge, decisional conflict, decision self-efficacy) among patients pre- and post-use of the DA in a multivariable linear regression model controlling for up to 5 independent covariates (e.g. age, stage of fibrosis, health literacy). We intend to include knowledge, decisional conflict, and decision self-efficacy as primary outcomes in three separate multivariable models, age and stage of fibrosis as planned covariates in all models. Health literacy will be included as a covariate in the model with knowledge as an outcome. Others will be added if significant at the bivariate level. The knowledge scale that we develop will be pilot tested with patients as well. We will assess scale reliability using Cronbach’s alpha.

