8.2 Bias

8.2.1 Methods to Minimize Bias

During the pilot phase (Aim 2), there is a chance of social desirability bias occurring. Social desirability bias is a type of response bias where participants give answers that are more favorable to the interviewer. We will reduce this bias by choosing the wording for our questions and materials carefully, using validated measures when available for Aim 2, assuring them there are no right or wrong answers, and reminding them that we are here to learn from them.

Confounding is often mentioned as a “mixing of effects” wherein the effects of the exposure under study on a given outcome are mixed in with the effects of an additional factor (or set of factors) resulting in a misrepresentation of the true relationship [61]. We controlled for confounding during study planning, where we specified our inclusion criteria and will control at the time of analysis by computing a multi-variable regression analysis.

We also selected a repeated measures/within subject design to minimize potential bias of a randomized trial randomizing at the patient level, where clinicians could contaminate the control group if they learned communication techniques after using the DA and applied them to controls as well.

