8.2.3 Limitations

- Aim 2 is a single site study with a moderate sample size, so results might not be generalizable. To address this, we plan to include a national sample of clinicians in Aim 3.
- Since there is no use of randomization in Aim 2, results should be interpreted as demonstrating preliminary efficacy of the tool. For example, we will not know if there were learning effects of taking the same measures twice or whether the DA led to changes in pre-post test outcomes. We will compare results to other studies of DAs and will design future larger studies with a control group for comparison.

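### Knowledge scoring gives zero to both unsure and wrong answers, so fewer unsure answers after the decision aid could raise a primary outcome without learning, and no planned analysis would show it

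*Combined protocol and SAP*

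**What the plan says.** Section 4.1 defines the knowledge measure. On format: "Questions will be asked using true/ false/ unsure responses". On scoring: "One point will be given for each correct response and zero for unsure or incorrect responses", and "answers will be expressed as percent correct". The items are still to be developed. The section adds that similar scales have been used in other decision aid trials.

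Section 8.1 gives knowledge its status: "We intend to include knowledge, decisional conflict, and decision self-efficacy as primary outcomes in three separate multivariable models". Its model adjusts for age, stage of fibrosis and health literacy. Scale reliability is to be assessed with Cronbach's alpha.

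The comparison is before against after in a single group. Section 3.1: "A quasi-experimental design was chosen to examine within group (pre-post use of the DA) outcomes". Section 6.1.1.1: "After viewing the DA, patients will complete post-test measures of knowledge, decisional conflict, and decision self-efficacy".

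Section 8.2.3 accepts that, without randomization, "we will not know if there were learning effects of taking the same measures twice". It does not mention guessing or a change in use of the unsure option. No section plans a guessing correction, a separate count of unsure and incorrect answers, or a sensitivity analysis on this point.

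**The concern.** The scoring rule is not neutral between declining to answer and guessing. Unsure scores 0 for certain. A guess on a true/false item scores 1 or 0, so exchanging unsure for a guess can never lower the score and on average raises it. If patients are more willing to commit to an answer after the decision aid, percent correct goes up whether or not they learned the content.

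The rule also hides the opposite result. A patient who goes from unsure to wrong moves from 0 to 0. For a tool meant to prepare patients for complex treatment discussions, a rise in wrong answers would matter, and percent correct alone could not reveal it.

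At stake is whether a pre-post rise on this primary outcome can be described as a gain in knowledge.

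**Working it through.** **1. The plan's own figure.** None is given for knowledge. Section 8.3 sizes the study on decisional conflict: N = 70, effect size 0.35, two-sided 5%, 80% power, paired t-test. The normal approximation is ((1.960 + 0.842)/0.35)² = 64.07, so 65 patients. The exact paired t-test needs 67 (power 80.6%), and N = 70 gives 82.3%. So 70 is sufficient for that outcome, and nothing below depends on it.

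**2. Inputs.** From the documents: response format, scoring rule and percent scale (4.1); primary status (8.1); single-group pre-post design (3.1, 6.1.1.1); N = 70 (8.3). Assumed, because not stated:
- p, the chance that a guess is right: 0.5 for a blind guess
- u, the share of items marked unsure at pre-test
- s, the share of those that become guesses at post-test
- K, the number of items: 8, borrowed from the number of review questions inside the decision aid (3.1, Table 1)
- the SD of test-retest noise: 10 to 25 points

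**3. One item.** Moving from unsure to a guess changes the expected score as follows.
- Percent-correct scoring: p − 0 = 0.5
- Correct minus incorrect: p − (1 − p) = 2p − 1 = 0

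**4. The whole test.** Expected gain with no learning = 100 × u × s × 0.5 points.

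| Share of items moved (u × s) | Gain in percent correct | Change in correct minus incorrect |
|---|---|---|
| 10% | 5 | 0 |
| 20% | 10 | 0 |
| 30% | 15 | 0 |
| 40% | 20 | 0 |

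Over u = 0.1 to 0.5 and s = 0.25 to 1, the gain runs from 1.25 to 25 points.

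**5. What each report would show.** Suppose that at pre-test 40% of answers are correct, 20% incorrect and 40% unsure.

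| Unsure items that become guesses | Correct | Incorrect | Unsure | Correct minus incorrect |
|---|---|---|---|---|
| none (pre-test) | 40 | 20 | 40 | 20 |
| 25% | 45 | 25 | 30 | 20 |
| 50% | 50 | 30 | 20 | 20 |
| 100% | 60 | 40 | 0 | 20 |

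The planned score reports only the first of these shares. The matching rise in incorrect answers is lost.

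**6. Would such a shift reach significance?** With g = u × s × 0.5, the standardized change is g / √(g(1 − g)/K + noise²). At K = 8 and N = 70:
- A 5-point artefact (g = 0.05) is 0.40 SD with noise of 10 points and 0.19 SD with noise of 25. A two-sided 5% paired test then rejects with probability 0.90 and 0.35.
- A 10-point artefact (g = 0.10) gives 0.69 and 0.37 SD, and rejects with probability 0.86 or more across that noise range.

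A simulation of 4,000 runs (u = 0.4, s = 0.5, noise SD 15, no learning) rejected in 99.5% of runs with percent correct and in 4.8% with correct minus incorrect. It used a paired t-test rather than the planned regression, and gave both scores the same noise. It illustrates one scenario.

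**7. If answers are better than blind.** With p = 0.6, moving 10% of items adds 10 × 0.6 = 6 points to percent correct and 10 × (2 × 0.6 − 1) = 2 points to correct minus incorrect. Partial learning therefore still registers in the sensitivity score, and only the blind component drops out.

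**8. The decision rule.** With no learning, the expected change in correct minus incorrect is 0, so its sign is positive about half the time. A same-direction rule would therefore pass the artefact about half the time. Requiring the 95% confidence interval to lie above zero passes it about 2.5% of the time.

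**The case against.** The scoring is fully specified, contradicts nothing in the plan, and follows a format that section 4.1 says other decision aid trials have used. Offering an unsure option already gives patients an alternative to guessing. All of that stands: this is a limit on interpretation, not an error.

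The behavioural step is also not in the documents. Section 1.1 describes decision aids as increasing knowledge and reducing indecision about treatment, and the self-efficacy scale in section 4.1 concerns confidence in decision-making actions, not certainty about facts. Nothing shows that this aid would produce blind guessing, and an answer given straight after reading the content is often partly informed. This stands too, and it makes the size conditional.

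The existing safeguards answer less than they seem to. Section 8.2.3 limits what can be said about the cause of a change, not whether the change is knowledge. Adjusting for health literacy does not separate known from guessed answers, and Cronbach's alpha measures consistency. Section 8.1 plans descriptive frequencies on all variables, which might include item responses, but does not say so. A later controlled study would remove only a retest shift. A shift caused by the aid would remain.

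A reader might also infer from section 8.2.1, where patients are reassured by "assuring them there are no right or wrong answers", that they are misinformed about the knowledge test and pushed towards guessing. The text does not support that. The assurance is a remedy for social desirability bias and is not tied to the knowledge items. Nothing says that it differs between pre-test and post-test, and it could equally make unsure more acceptable. At most its scope needs stating.

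**Conclusion.** The point holds in conditional form. If unsure answers give way to guesses after the decision aid, percent correct rises by 0.5 times the share of items moved with no learning: 5 points for 10% of items, 20 points for 40%. This rests on a blind guess being right half the time. The share moved is unknown, so these figures are a range of scenarios and not an estimate of bias. Moves from unsure to wrong are invisible whatever the share.

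A reader might infer that the knowledge result will be inflated, or that the trial's primary result is unsafe. The documents support neither. They give no unsure rate and no evidence of guessing; knowledge is one of three primary outcomes; and the sample size rests on decisional conflict. What they do support is that the planned analysis could not distinguish such a shift from learning. This is a cheap improvement to make while the items are still being written.

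**What to change.** Keep percent correct as the stated score. In sections 4.1 and 8.1 add:

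1. A table of percent correct, percent incorrect and percent unsure, before and after the decision aid.
2. A pre-specified sensitivity analysis of the paired change in correct minus incorrect, with its 95% confidence interval.
3. A reporting rule: describe the result as a knowledge gain without qualification only if that interval lies above zero. Agreement in direction alone is not enough. Otherwise, report that the rise may reflect fewer unsure answers.

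Optional and secondary: state in section 8.2.1 that the reassurance about answers applies to the attitude and values items. At both pre-test and post-test, give the same instruction to mark unsure on any knowledge item the patient does not know.

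The cost is one table and one extra analysis from item responses already being collected, plus a sentence of instructions if the optional step is taken. Correct minus incorrect may be noisier than percent correct, and the knowledge gain may look smaller. The table shows how many answers turned wrong but not how confidently they were held, because item confidence is not measured.

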8.3 Sample Size and Power Calculations

Sample size and power were calculated using Power Analysis and Sample Size Software (PASS 11) [53]. We conducted our sample size calculation based on our expected change in decisional conflict based on past studies using DAs overall [54], and by consulting with the scale's user manual [55]. We expect a 15 point reduction in decisional conflict scores pre- and post- use of the DA and an effect size of 0.35. To examine within group differences in decisional conflict among patients pre- and post-use of the DA, we will conduct a paired-samples t-test. A sample size of 70 patients allows us to achieve a power of 80%, using two-sided t-test with a type I error of 5%.

We will also examine within group differences in our outcomes among patients pre- and post-use of the DA in a multivariable linear regression model controlling for up to 5 independent covariates (e.g. age, health literacy, race/ethnicity, decision role preference, clinical characteristics).

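### Does the plan need a paired analysis of patients crossing the SURE cut-off of 4, in addition to its test of mean change?

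*Combined protocol and SAP*

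**What the plan says.** Section 4.1 describes the SURE Test as four items scored 1 or 0, so the total runs from 0 to 4. It adds: "If the total score is less than 4, it indicates the probability that a patient experiences clinically significant decisional conflict". No later section uses this cut-off.

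Section 3.1 lists the change in decisional conflict among the Aim 2 outcomes and states that "our goal is to demonstrate feasibility and preliminary efficacy". Section 6.1.1.1 has the same patients measured before and after the decision aid: "After viewing the DA, patients will complete post-test measures of knowledge, decisional conflict, and decision self-efficacy".

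On analysis, section 8.3 says of the before/after comparison of decisional conflict that "we will conduct a paired-samples t-test". Section 8.1 adds: "We intend to include knowledge, decisional conflict, and decision self-efficacy as primary outcomes in three separate multivariable models". It also promises that "descriptive statistics (e.g., frequencies, tendencies, variability) and diagnostic plots will be completed on all variables".

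**The concern.** Only a score of 4 lies outside the range that section 4.1 associates with conflict. A gain from 1 to 2 and a gain from 3 to 4 count equally in a mean, but only the second takes the patient out of that range. A highly significant t-test could therefore coexist with almost nobody crossing the threshold.

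Separate before and after frequencies repair part of this, because they show the net change in the number below 4. They do not show how many patients left the range and how many entered it, and the interval for a paired difference depends on those two counts. The fear is that a reader of a pilot on preliminary efficacy would see a net shift across the plan's own cut-off without its precision, and that any interval supplied later would be post hoc.

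**Working it through.** **Inputs.** SURE range 0 to 4 and cut-off below 4 (section 4.1). Effect size 0.35, two-sided 5%, power 80%, N=70, paired t-test (section 8.3). Frequencies on all variables (section 8.1). The documents give no SURE distribution, so every score pattern below is an assumption.

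**1. The plan's own figure.** Normal approximation: n = ((1.960 + 0.842)/0.35)² = 64.1, so 65. The noncentral t distribution (df n−1, noncentrality 0.35√n) gives n = 67, and N=70 gives 82.3% power. In standardised units the sample size therefore supports the test of mean within-patient change, with a small margin.

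**2. Question against analysis.** The outcome in section 3.1 is a change. Sections 8.1 and 8.3 analyse a within-patient change. The sentence in section 4.1 says how one patient's score is read. It defines no responder endpoint, and no section sets out to estimate a proportion. The question and the named analysis match.

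**3. Can the mean mislead about the cut-off?** On its own, yes. Take two sets of 70 pairs, each with mean change 24/70 = 0.343, SD 0.478 and the same t-test result (p < 0.001). In one, 24 patients move from 1 to 2 and none crosses. In the other, 24 move from 3 to 4 and all cross. The planned frequencies tell them apart: below 4 goes from 50 to 50 in the first and from 50 to 26 in the second.

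A pair with an identical baseline (16, 20, 18 and 16 patients at scores 4, 3, 2 and 1) and mean gain 42/70 = 0.6 behaves the same way. The t statistics are 5.85 and 5.63, while the number below 4 goes from 54 to 34 in one and from 54 to 53 in the other. Again the frequencies separate them.

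**4. What the frequencies leave open.** Fix the margins at 50/70 below 4 before and 40/70 after, a net fall of 10/70 = 14.3 points. Let b be the number resolved and c the number worsened, with b − c = 10. The before/after correlation is φ = [(50−b)(20−c) − bc]/√(50·20·40·30), with denominator 1095.4.

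| b / c | φ | 95% CI, points (Tango score) |
|---|---|---|
| 10 / 0 | 800/1095.4 = 0.73 | 7.9 to 24.3 |
| 14 / 4 | 520/1095.4 = 0.47 | 2.6 to 26.4 |
| 20 / 10 | 100/1095.4 = 0.09 | −1.1 to 29.1 |

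The frequencies are identical in all three rows, and only the last interval includes zero.

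**5. How extreme must that be?** The paired Wald standard error is √[(b+c) − (b−c)²/70]/70. The lower limit falls below zero when 10 < 1.96·√(b+c−1.43), that is b+c > 27.5. Since b+c = 10+2c, this means c ≥ 9. At c = 9, φ = (31·11 − 19·9)/1095.4 = 170/1095.4 = 0.16. So 9 of the 20 patients who start at 4 would have to drop into the conflict range after viewing the aid, with almost no association between two administrations of the same four items in a session that section 6.1.1.1 expects to last 30 to 45 minutes.

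**6. Precision from the margins alone.** The unpaired standard error is √[(0.714·0.286 + 0.571·0.429)/70] = 0.080, giving 14.3 ± 15.7, or −1.4 to 30.0 points. When the before/after correlation is not negative, this interval is conservative for the paired difference.

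**The case for a change.** The strongest case for the concern is that decisional conflict is a primary outcome and the basis of the sample size, that the cut-off is the only clinical reading the plan gives the score, and that the paired data are collected anyway. Two or three sentences in section 8.1 would add the table and its interval. The general clause in section 8.1 on robust methods and data reduction does not cover it, because it applies only if problems are found and names no cut-off.

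All of that is factually right. No paired table is named, and separate frequencies do not fix the split. The unpaired interval in step 6 includes zero even where the paired one would not, so some precision is lost.

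What does not follow is that the plan is deficient. The mean comparison stays valid, and no go/no-go decision rests on the proportion crossing 4. The extra analysis would also say little at this size. The intervals in step 4 are 16 to 30 points wide. Exact McNemar power at N=70 is 37% for assumed rates of 15% resolved and 5% worsened, 67% for 20% and 5%, 86% for 25% and 5%, and 49% for 25% and 10%. Section 8.2.3 already concedes that without a control group "we will not know if there were learning effects of taking the same measures twice", so an interval for the crossing proportion could not be read as an effect of the decision aid in any case.

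**Conclusion.** The concern does not hold. Carried out as written, the plan answers its own question about change in decisional conflict, and its descriptive statistics show the number below 4 at each time. What is missing is the split into resolved and worsened patients and a paired interval. That is a supportive table one might like to see, and its absence makes no planned result invalid. In the constructed example, the missing split changes whether the interval includes zero only when the before/after correlation is about 0.16 or lower.

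This rests on assumed score distributions, on a before/after correlation that is clearly positive, and on the result being read as preliminary efficacy from an uncontrolled pilot. It also assumes that the 0 to 4 SURE score is the one used. Section 8.3 says "We expect a 15 point reduction in decisional conflict scores", which cannot occur on a 0 to 4 score. That is a separate inconsistency which this conclusion neither resolves nor excuses.
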